7 STUDY SCHEDULE

Subjects with CB at 24 weeks (Visit 6) will continue on therapy as long as they are still benefitting from the treatment. Treatment may continue for up to 24 months from the date of randomization (as long as they continue to demonstrate CB from the treatment during these 24 months).

Subjects who continue to demonstrate a CB from the study treatment at 24 months will be offered to continue in a safety extension study under a separate protocol.

All visits may be scheduled within a time window of \pm 7 days.

7.1 Screening

Screening assessments must occur within 28 days prior to randomization for determination of subject's overall eligibility. Informed consent will be obtained from the subjects before any other study procedure or test. AEs will be collected from the signing of the informed consent form (ICF). The following tests and procedures will be performed during the screening visit (Visit 1):

- Eligibility criteria check
- Subject medical history (current and past)
- Demography (age, gender, race)
- Diagnosis and extent of cancer
- Review of prior/concomitant medications, including previous and current anticancer treatment
- Physical examination, including height, weight, and vital signs (heart rate, respiratory rate, body temperature, blood pressure in a sitting position)
- ECOG performance status
- ECG

Compound No.: GTx-024 Author: [name]

- Blood sampling for: screening for HIV, HBV, and HCV
- Blood sampling for: hematology, biochemistry, coagulation status, and serum pregnancy test
- Blood sampling for specific blood tests: PSA
- Urine analysis
- AE collection (from the moment of ICF signing)
- Radiological evaluation of the BC (as applicable CT/MRI/bone scan). Imaging
 results will be confirmed by a central imaging facility blinded to the dose of
 GTx-024 to be received, although a subject will be enrolled based on the local
 imaging and Investigator's assessment. The central imaging facility will also
 perform tumor volumetric assessment for the subjects undergoing CT scanning. It
 is recommended these procedures are done as close to the randomization visit
 (Visit 2) as possible (if possible within 7 days prior to randomization)
- Review of medical history to confirm the hormonal receptor status of the tumor (ER, HER2). ER status will be confirmed by a local laboratory if not available in the subject's medical history. AR status will be confirmed at a central laboratory
- Eye examination including best corrected distance visual acuity with refraction, intraocular pressure, slit lamp examination, and dilated fundus photography (must be completed between Day –28 and Day –1)

7.2 Randomization/Baseline

The following tests and procedures will be performed during the randomization/baseline visit (Visit 2), or results checked and confirmed:

- Eligibility criteria checked; prior to randomization
- Review of prior/concomitant medications, including previous and current anticancer treatment
- Vital signs (heart rate, respiratory rate, body temperature, blood pressure in a sitting position), if not done within the last 7 days

Compound No.: GTx-024 Author: [name]

- ECOG performance status, if not done within the last 7 days
- Blood sampling for: hematology, biochemistry, and PSA, if not done within the last 7 days; and serum lipid profile, serum hormones, and CTCs (enumeration and gene expression)
- Urine analysis, if clinically indicated
- AE collection
- Subjects will be asked to complete a QoL questionnaire (EQ-5D-5L; before initiation of treatment)
- Randomization
- The first dose of study drug will be administered at this visit. Subjects will be given a carton box of 7 blister packs containing GTx-024
- Blood sample for pharmacokinetic assessment. The baseline blood sample should be collected before the subject is given their first dose of GTx-024. The exact time (hh:mm) and date of the blood sample will be recorded on the eCRF.

7.3 Treatment Phase

The first dose of study drug will be administered on the day of randomization (Visit 2). GTx-024 will be administered daily for up to 24 months from randomization or until disease progression (whichever is sooner), subject's withdrawal of consent, or intolerability.

During the study treatment phase, the subjects will be scheduled for a visit every 6 weeks. Visit 7 at week 28 will only take place in subjects who have CR or PR at Visit 6 (week 24; see below).

The following tests and procedures will be performed during Visits 3, 4, 5, and 6 (weeks 6, 12, 18, and 24) in the treatment phase:

Review concomitant medications

Compound No.: GTx-024 Author: [name]

- Physical examination, including weight and vital signs (heart rate, respiratory rate, body temperature, blood pressure in a sitting position)
- ECOG performance status
- Blood sampling for: hematology, biochemistry, serum lipid profile, coagulation status, serum hormones, and PSA
- Urine analysis, if clinically indicated
- AE collection
- Subjects will be asked to complete a QoL questionnaire (EQ-5D-5L)
- GTx-024 drug accountability/dispensation

Radiologic assessments for anti-tumor effect will be done every 12 weeks whilst subjects receive treatment (Visits 4, 6, and thereafter). The same imaging technique must be used throughout the study in a given subject. Bone scans will be performed at screening and then every 12 weeks whilst subjects receive treatment (Visits 4, 6, and thereafter) in only those subjects with baseline bone metastases, or if clinically indicated. In addition, if any subject has CR or PR at Visit 6 (week 24), in compliance with RECIST 1.1 guidelines, a confirmation of the CR or PR (CT/MRI/bone scan) should be done 4 weeks later (Visit 7; week 28). The central imaging facility will also perform tumor volumetric assessment for the subjects undergoing CT scanning during Visits 4 and 6 (weeks 12 and 24). Blood sampling for CTC enumeration will be done at the same visits as the radiological assessments during the treatment phase; i.e., every 12 weeks whilst subjects receive treatment (Visits 4 and 6), but not at the confirmation of the CR or PR visit (Visit 7; week 28) or at Visits 8–13.

Dispensing of GTx-024 will be done at all study visits (except Visit 7) during the treatment phase (every 6 weeks at Visits 3, 4, and 5). At Visits 6, 8, 9, 10, 11, 12, and 13, in order to accommodate the visit schedule of every 12 weeks (± 7 days), the subjects will receive two carton boxes of study drug (each containing 7 blisters) to cover study treatment for 14 weeks.

Compound No.: GTx-024 Author: [name]

At any time point during the treatment period, if clinically indicated, an eye examination including any or all of the following procedures will be performed based on medical judgment: best corrected distance visual acuity with refraction, intraocular pressure, slit lamp examination, and dilated fundus photography.

Blood samples for pharmacokinetic assessment will be collected at Visit 3 (week 6), Visit 5 (week 18), and Visit 6 (week 24). The exact time (hh:mm) and date of each blood sample will be recorded on the eCRF. The date and approximate time of the last dose of GTx-024 prior to the blood sample should also be recorded; i.e., it should be documented whether the subject took the previous dose that morning or the evening before.

7.4 End of Treatment (EOT) Visit

For all subjects the EOT visit should happen as soon as possible after the last dose of GTx-024 has been taken and no later than 3 days after that. The following tests and procedures will be performed during the EOT visit:

- Review of concomitant medications
- Physical examination, including weight and vital signs (heart rate, respiratory rate, body temperature, blood pressure in a sitting position)
- ECOG performance status
- Blood sampling for: hematology, biochemistry, serum lipid profile, coagulation status, and serum hormones
- Blood sampling for specific blood tests: PSA and CTCs (enumeration and gene expression)
- Urine analysis, if clinically indicated
- AE collection
- Radiological evaluation of the BC (as applicable CT/MRI/bone scan). Imaging results will be confirmed by a central imaging facility blinded to the GTx-024 dose.

Compound No.: GTx-024 Author: [name]

The same imaging technique must be used throughout the study in a given subject.

- Subjects will be asked to complete a QoL questionnaire (EQ-5D-5L)
- GTx-024 drug accountability
- Eye examination including best corrected distance visual acuity with refraction, intraocular pressure, slit lamp examination, and dilated fundus photography

7.5 Post-treatment Follow-up

Subjects will be followed up for 1 month after the last dose of GTx-024. They will undergo the following procedures:

- Review of concomitant medications
- Physical examination, including weight and vital signs (heart rate, respiratory rate, body temperature, blood pressure in a sitting position)
- ECOG performance status
- Blood sampling for: hematology and biochemistry
- Blood sampling for PSA
- Urine analysis, if clinically indicated
- AE collection

7.6 Early Termination Visit

An early termination visit will happen in case of:

- A subject withdrawing from the study at their discretion
- GTx, Inc. terminating the study in the interest of subject welfare
- Investigator withdrawing the subject from the study

Subjects will be asked to attend a final visit so that the procedures for the EOT (see above) may be performed.

Compound No.: GTx-024 Author: [name]

7.7 Unscheduled Visit

A page will be included in the eCRF that asks about whether any unscheduled visits have taken place and provides space for the recording of any collected data, including unscheduled vital signs, ECGs, and laboratory results on the unscheduled visit eCRF page. Early/late planned visits will not be considered to be unscheduled visits.

Compound No.: GTx-024 Author: [name]

8 STUDY PROCEDURES/EVALUATIONS

Please see the APPENDIX A: SCHEDULE OF EVENTS for an outline of the timing of the study procedures/evaluations.

8.1 Clinical Evaluations

All treatment decisions will be based on Investigator assessments, including determination of PD.

Imaging Assessments:

CT with contrast of the chest, abdomen, and pelvis including the liver and the adrenals will be performed to assess tumor status. If contrast is contraindicated, CT without contrast for chest and pelvis and MRI of the abdomen should be performed. Whichever imaging method is selected should be used for all study assessments in a given subject.

Bone scintigraphy (bone scans) will be performed to assess bone metastases. Bone scans will be performed at screening and then every 12 weeks whilst subjects receive treatment (Visits 4, 6, and thereafter) in only those subjects with baseline bone metastases, or if clinically indicated.

Tumor lesions will be assessed using RECIST 1.1 at the site based on the local reading facility. Scans will be sent to the central imaging facility, blinded to the GTx-024 dose, for final efficacy outcomes analysis.

In compliance with RECIST 1.1, if any subject has CR or PR at Visit 6 (week 24), a confirmation of the CR or PR (CT/MRI/bone scan) should be done 4 weeks later (Visit 7; week 28).

Tumor volumetrics will be performed by the assigned central vendor only for subjects who have CT scans at screening and then at weeks 12 and 24 (Visits 4 and 6). Tumor volumetrics will be performed by an independent 3rd party vendor who is masked to individual subject treatment and outcomes.

Compound No.: GTx-024 Author: [name]

Medical History and Medication History:

The medical history of the subject will be obtained by the PI from the subject's medical record. The medical history will include a review of the hormonal status of the BC (ER, HER2).

Medication history will include all medications currently being taken (rather than the lifelong medication history) and will include both prescription and over-the-counter medicines (also including nutritional supplements or herbal treatments). This will include prior cancer treatments taken.

Demographics:

The following demographic data will be collected: age, gender, and race.

Physical Examination:

Physical examination will include organ palpation, lymph nodes palpation, skin turgor, and muscle weakness measurement.

Height and weight will also be measured as outlined in the schedule of events.

AEs will be followed-up to resolution, and while further physical examinations may take place, they will not be mandatory.

Vital Signs:

Vital signs at scheduled visits will include body temperature, respiratory rate, blood pressure, and heart rate. Vital signs may be taken at any other times. Blood pressure and heart rate measurements will be performed with subjects in a seated position.

ECOG Performance Status:

ECOG performance status will also be measured (see APPENDIX B: ECOG PERFORMANCE STATUS).

Compound No.: GTx-024 Author: [name]

ECG:

A standard 12-lead ECG will be performed at screening. Tracings must be dated and signed by the Investigator (or his/her designee) and filed with the subject's source documentation. Results from 12-lead ECG should be captured on the ECG Evaluation eCRF. Significant findings must be recorded as Relevant Medical History/Current Medical Conditions (if present before treatment). ECG may be repeated at the discretion of the Investigator at any time during the study and as clinically indicated; any clinically relevant findings should be added to the AE eCRF.

Interpretation of the tracing must be made by a qualified physician. Each ECG tracing should be labeled with the study number, subject initials (where regulations permit), subject number, and date, and kept in the source documents at the study site. Clinically significant abnormalities present when the subject signed informed consent should be reported on the Medical History eCRF page. Clinically significant findings must be discussed with the Medical Monitor prior to randomizing the subject in the study. The PI will take the final decision if any observed deviations in the ECG are sufficient to require that the subject be excluded from the study.

Eye examination:

An eye examination will be performed at screening, as clinically indicated during the treatment phase, and at EOT. The eye examination should include best corrected distance visual acuity with refraction, intraocular pressure, slit lamp examination, and dilated fundus photography.

QoL (EQ-5D-5L):

Subjects will complete the EQ-5D-5L at the time points as per the schedule of events.

The EQ-5D-5L is a standardized instrument to measure health outcome. It is applicable to a wide range of health conditions and treatments, and provides a simple descriptive profile and a single index value for health status. The EQ-5D-5L takes only a few minutes to complete. Instructions to respondents are included in the

Compound No.: GTx-024
Author: [name]

questionnaire. An EQ-5D-5L self-complete version was designed to increase sensitivity and reduce ceiling effects. This is available in paper format.

8.2 Laboratory Evaluations

8.2.1 Clinical Laboratory Evaluations

All tests listed below (Table 1) will be performed by a central laboratory as per APPENDIX A: SCHEDULE OF EVENTS. In addition, laboratory safety tests may be performed at various unscheduled time points, if deemed necessary by the PI. Hematological and biochemistry tests will be performed at screening, at baseline (only if screening was done longer than 7 days before start of the treatment), at each visit during the treatment phase (except Visit 7), or as medically necessary, and at the discontinuation from study treatment (within 3 days after discontinuation).

A serum lipid profile includes: total cholesterol, low-density lipoprotein (LDL), HDL, and triglycerides. This assessment will be performed at baseline; at Visits 3, 4, 5, and 6 (weeks 6, 12, 18, and 24) and Visits 8–13 (every 12 weeks ± 7 days if still on treatment after week 24) during the treatment phase; and at EOT.

INR and aPTT are examined as coagulation assessments. They will be performed at screening (and checked at the baseline visit only if screening was done longer than 7 days before start of the treatment); at Visits 3, 4, 5, and 6 (weeks 6, 12, 18, and 24) and Visits 8–13 (every 12 weeks \pm 7 days if still on treatment after week 24) during the treatment phase; and at EOT.

Serum hormones include: testosterone, estradiol, and SHBG. This assessment will be performed at baseline; at Visits 3, 4, 5, and 6 (weeks 6, 12, 18, and 24) and Visits 8–13 (every 12 weeks ± 7 days if still on treatment after week 24) during the treatment phase; and at EOT.

Any particular clinical findings seen before taking study treatments must be documented in the Relevant Medical History/Current Medical Conditions eCRF.

Compound No.: GTx-024 Author: [name]

Findings compatible with AEs after taking study treatment must be documented in the AE eCRF.

Urinalysis includes macroscopic and microscopic examinations. Macroscopic examination includes: specific gravity, pH, protein, glucose, bilirubin, ketones, blood cells, and leukocytes. Microscopic examination includes: white blood cells (WBC)/high power field (HPF), red blood cells (RBC)/HPF and any additional findings. Urinalysis will be performed only at screening and if medically indicated.

Significant findings must be recorded as Relevant Medical History/Current Medical Conditions (if present before treatment). Urinalysis may be repeated at the discretion of the Investigator at any time during the study and as clinically indicated; any clinically relevant findings should be added to the AE eCRF.

The categories of subjects listed in Section 5 Study Enrollment and Withdrawal should be tested for hepatitis B serologic markers and viral load at screening: HBV-DNA, HBsAg, HBcAb, and HBsAb. Subjects with hepatitis C risk factors and additional subjects at the discretion of the Investigator should be tested for HCV ribonucleic acid-polymerase chain reaction (RNA-PCR) test at screening. For a list of hepatitis C risk factors, refer to Section 5.

HIV, HBV, and HCV screening will be performed at screening for all subjects. If a subject test is positive for HIV, HBV, or HCV, she will be considered ineligible for the study according to the Exclusion Criteria. Please note that subjects whose test is negative for HBV-DNA, HBsAg, and HBcAb but positive for HBsAb with prior history of vaccination against Hepatitis B will be eligible. The fact that the subject had been vaccinated should be entered into the subject's Medical History eCRF. Results will not be reported in the eCRF.

Compound No.: GTx-024 Author: [name]

Table 1: Clinical Laboratory Tests

Hematology	Serum Chemistry
Hemoglobin	Blood Urea Nitrogen
Hematocrit	Bilirubin (total and direct)
Total and differential leukocyte	Alkaline phosphatase
count	• AST
RBC count	• ALT
Platelet count	Albumin
	Sodium
	Potassium
	Creatinine
Urinalysis	Additional Tests
• pH	HIV test
Specific gravity	HBV-DNA
Protein*	HBsAg
• Glucose	HBcAb
 Ketones 	HBsAb
Bilirubin	• HCV
Blood*	 Serum lipid panel (total cholesterol, LDL,
Nitrite*	HDL, triglycerides)
Urobilinogen	 Coagulation tests (INR, aPTT)
Leukocyte esterase*	 Serum pregnancy test
•	• PSA
	 Hormonal status of the tumor (AR)
	• CTCs
	Blood hormone levels, including testosterone,
	estradiol, SHBG
* If urinalysis is positive for protein, blood, i	nitrite, and/or leukocyte esterase, a microscopic

Compound No.: GTx-024 Author: [name]

8.2.2 Special Assays or Procedures

Pharmacokinetic assessment:

Blood samples for pharmacokinetic assessment will be collected at baseline (pre-dose), Visit 3 (week 6), Visit 5 (week 18), and Visit 6 (week 24). One blood sample will be collected in a 6 mL K2-ethylenediaminetetraacetic acid (EDTA) blood collection tube on each of these days. The exact time (hh:mm) and date that each blood sample is collected will be recorded on the eCRF. At the baseline visit, the blood sample should be collected before the subject is given their first dose of GTx-024. At visits 3 (week 6), 5 (week 18), and 6 (week 24), the date and approximate time of the last dose of GTx-024 prior to the blood sample should be recorded; i.e., it should be documented whether the subject took the previous dose that morning or the evening before. Immediately after collection, the tubes will be gently inverted several times to mix the anticoagulant with the blood sample.

Blood samples will be kept on wet ice (ice packs in a water bath is also acceptable) for up to 20 minutes until processed. The plasma fraction will be separated by placing the collection tube into a centrifuge for 10 minutes at 1,500 x g. The plasma fraction will be withdrawn by pipette and divided into two 2 mL polypropylene transfer vials (with each tube receiving approximately equal aliquots).

All sample collection and freezing tubes will be clearly labeled in a fashion which identifies the subject, the study number, the visit number, and freezing tube aliquot letter. Labels will be fixed to freezing tubes in a manner that will prevent the label from becoming detached after freezing. Samples will be stored in a freezer at –20°C or lower. Samples will be shipped in a thermal insulated container with sufficient dry ice to assure they remain frozen.

Any remaining plasma samples after completion of the protocol outlined pharmacokinetic analysis may be used to identify and quantify the metabolites of GTx-024.

Compound No.: GTx-024 Author: [name]

Circulating Tumor Cells (CTCs):

Blood samples will be collected for CTC enumeration at Visits 2, 4, 6, 8, and EOT and for gene expression at Visit 2 and EOT.

The enumeration sample will be collected in a 10 mL CellSave tube.

The gene expression sample will be collected in a 10 mL EDTA blood collection tube.

All CTC samples are to be stored under ambient conditions and shipped on the same day of collection. CTC enumeration testing is to be completed within 96 hours of collection and gene expression within 36 hours of collection.

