6.1.2 Formulation, Packaging, and Labelling

GTx-024 3.0 mg Softgels will be supplied as opaque, white to off-white, size 5, oval Softgel capsules with "GTx" imprinted in black ink on the outer shell containing 3.0 mg of GTx-024. The liquid Softgel fill is composed of GTx-024 dissolved in polyethylene glycol 400. GTx-024 3.0 mg Softgels will be packaged in blister packs. Each blister pack will contain sufficient study drug for one (1) week of dosing. At randomization (Visit 2) and at Visits 3, 4, and 5), subjects will be provided with a carton of study drug containing 7 blister packs, equivalent to 7 weeks of dosing. At Visits 6, 8, 9, 10, 11, 12, and 13, in order to accommodate the visit schedule of every 12 weeks (± 7 days), the subjects will receive two carton boxes of study drug (each containing 7 blisters) to cover study treatment for 14 weeks. Subjects will be requested to bring with them the carton box with all blister packs at every visit.

Each blister pack will be comprised of an appropriate number of blister strips (1 blister for the 9 mg treatment arm and 2 blisters for the 18 mg treatment arm) encased in a child-resistant heat-sealed card. The blister strips are composed of a PVC/ACLAR base and an aluminum foil/PVC/PVAC copolymer and polymethacrylate (product contact) lidding. Perforations on the back of the heat-seal card overlay the foil lidding. To remove the study drug, subjects will release the appropriate perforation by depressing a release button on the inside of the card. Once released, the perforation can be removed and the study drug pushed through the foil.

Compound No.: GTx-024 Author: [name]

Dosing instructions will be provided on the study drug label and in the subject information sheet.

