6.2 Dosage, Preparation, and Administration of Study Investigational Product

Three (3) GTx-024 3.0 mg softgels for a 9 mg daily dose or six (6) GTx-024 3.0 mg softgels for an 18 mg daily dose will be taken PO with water at approximately the same time each day, with or without food.

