6.3 Modification of Study Investigational Product for a Subject

Subjects on the 9 mg treatment arm who experience an AE with Grade ≥ 3 intensity (NCI-CTCAE 4.0) and/or intolerance may have a drug interruption based on the medical judgment of the Investigator and after confirmation by the study Medical Monitor. The drug interruption may last for a period of up to 5 days after which the subject must be rechallenged with study drug (9 mg) or, as appropriate, subjects should be discontinued from study.

Subjects in the 18 mg treatment group who experience an AE with Grade \geq 3 intensity (NCI-CTCAE 4.0) and/or intolerance may have a dose reduction from 18 mg to 9 mg per day or a drug interruption based on the medical judgment of the Investigator and after confirmation by the study Medical Monitor. The drug interruption may last for a period of up to 5 days after which the subject must be rechallenged with study drug (18 mg or 9 mg) or discontinued from the study. In the case of a dose reduction, once the AE has resolved or reduced in intensity to Grade 1, the subject may be rechallenged with 18 mg or maintained at 9 mg at the discretion of the Investigator.

Compound No.: GTx-024
Author: [name]

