6.4 Accountability Procedures for the Study Investigational Product(s)

The Investigator is responsible for the correct storage of study medication according to GTx, Inc. recommendations. The study medication made available for this clinical trial must be used in accordance with the protocol and dispensed only under the supervision of the Investigator and documented sub-Investigators. The Investigator must maintain complete and accurate records, showing the receipt and disposition of all supplies of the study medication delivered by the GTx, Inc., authorized representative. These records must include a master record which lists the date of receipt of all study medication shipments, batch numbers, expiration date, and quantities received. In addition, a dispensing record which includes all quantities dispensed, identification of the person to whom study medication was dispensed, the date of each dispensing, and the identification of the dispenser will also be maintained. The master dispensing records are separate from records kept for individual trial subjects.

It is the Investigator's responsibility to ensure that study medication used by trial subjects plus unused study medication equal the total amount received from the GTx, Inc., authorized representative. Damaged and/or contaminated packets must also be accounted for in the dispensing records. All discrepancies must be explained in writing. The study personnel responsible for study medication administration to the subject will record the date and time the initial treatment is given to the subject. In addition, the Drug Accountability electronic case report form (eCRF) will document any treatment interruptions or discontinuations.

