11.4.3.4 Tertiary efficacy analysis

The following tertiary efficacy analyses will be performed in subjects in each of the 9 mg and 18 mg arms among the evaluable subjects and among the FAS:

- PSA changes from baseline to each scheduled assessment will be described and tested for a significant change from baseline. Percentage change from baseline will be summarized and analyzed as well
- QoL: The EQ visual analog scale (VAS) will be summarized by descriptive statistics at baseline and each assessment. Mean changes from baseline will also be summarized using descriptive statistics and 95% confidence intervals. EQ-5D-5L single item scale scores (mobility, self-care, usual activities, pain/discomfort, and anxiety/depression) will be summarized by means of frequency counts at baseline and at each assessment
- CTCs: Changes in the number of CTCs from baseline to each scheduled assessment will be described and tested for a significant change from baseline
- Duration of prior CB: The impact of duration of prior CB on the current CB
 response will be explored in an exploratory way using logistic regression models
 with and without other covariates. The impact of duration of prior CB on PFS, TTP,
 and duration of response outcomes will be assessed in a Cox proportional hazards
 model with and without other covariates
- Time from diagnosis of metastases to randomization: The impact of time from diagnosis of metastases to randomization on the current CB outcome will be explored in an exploratory way using logistic regression models with and without other covariates. The impact of time from diagnosis of metastases to randomization on PFS, TTP, and duration of response outcomes will be assessed in a Cox proportional hazards model with and without other covariates
- Tumor volumetrics: The effect of GTx-024 9 mg and 18 mg on tumor volume will be described visually using waterfall plots

Compound No.: GTx-024 Author: [name]

 GTx-024 and GTx-024 glucuronide plasma concentrations will be assessed for their association with CBR at week 24 using logistic regression by creating binary variables for the concentrations by dichotomizing at the median concentration at week 24

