11.4.3.6 Pharmacokinetic analyses

 Descriptive statistics will be used to summarize the plasma concentrations of GTx-024 9 mg and 18 mg and GTx-024 glucuronide at each assessment

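### PK samples at weeks 6, 18 and 24 have no set time relative to dose and the analyses ignore time after dose, so exposure groups partly reflect when blood was drawn (minor)

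*Combined protocol and SAP*

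**What the plan says.** Section 8.2.2 takes a single blood sample at baseline and at weeks 6, 18 and 24. Only the baseline sample is tied to dosing: it precedes the first dose. For the later three, the draw time is recorded to the minute. The last dose needs a date and an approximate time, which the text then explains as "it should be documented whether the subject took the previous dose that morning or the evening before". Section 7.3 and footnote 11 to the Schedule of Events (repeated in Appendix A) carry the same rule and add no sampling window.

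Section 6.2 has the capsules taken "at approximately the same time each day, with or without food", so a subject may dose in the morning or the evening.

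The values are used in two places. Section 11.4.3.6 states: "Descriptive statistics will be used to summarize the plasma concentrations of GTx-024 9 mg and 18 mg and GTx-024 glucuronide at each assessment". Section 11.4.3.4 relates concentration to week 24 clinical benefit by logistic regression within each arm, "creating binary variables for the concentrations by dichotomizing at the median concentration" at week 24. Neither mentions time after dose.

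On the amount taken, Section 6.3 lets 18 mg subjects with certain adverse events switch: they "may have a dose reduction from 18 mg to 9 mg per day or a drug interruption". The PK record does not ask how much was last taken. Section 6.4 says the accountability eCRF "will document any treatment interruptions or discontinuations".

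**The concern.** A once-daily drug has a concentration profile over the day. At a daytime visit, a subject who dosed that morning is a few hours past the dose. One who dosed the evening before is at very roughly 11–17 h. A morning doser who has not yet dosed is near 24 h, which fits neither category named in the text. Pooling these values makes a per-visit mean depend on the mix of dosing habits. A median split then ranks subjects partly by clock time. If sampling time is unrelated to benefit, this pulls the concentration–benefit odds ratio toward 1.

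Two stated aims use these data: the PK objective of describing concentrations at each time point, and the tertiary objective of relating concentration to the 24-week clinical benefit rate (CBR). A dose time or amount not collected at the visit is hard to recover later.

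**Working it through.** **Inputs from the protocol.** One sample per PK visit, 24 h dosing interval, no dose-relative window after baseline, up to 44 evaluable subjects per arm, median split within arm. The protocol gives no half-life, absorption rate, variability or peak-to-trough figure, so there is no stated result to reproduce.

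**Assumptions.** One-compartment oral model at steady state, absorption rate ka = 1.5/h, half-life 12–48 h. Sampling mix: 50% at 1–6 h after dose, 30% at 11–17 h, 20% not yet dosed at 22–26 h. Clearance CV 30% or 40%, with each subject's half-life varying with clearance; 15% residual error; 400,000 simulated subjects per case.

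**Concentration at time t after dose**, with k = ln 2 / half-life:

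C(t) ∝ e^(−kt)/(1 − e^(−24k)) − e^(−ka·t)/(1 − e^(−24ka))

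Example at a 24 h half-life (k = 0.0289, 1 − e^(−24k) = 0.5): C(3.5) ∝ 0.9039/0.5 − 0.0052 = 1.803 and C(14) ∝ 0.6674/0.5 = 1.335. The ratio is 1.35.

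**Misclassification.** A subject is misclassified when the observed concentration and the true AUC lie on opposite sides of their medians.

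| Half-life | Peak / 24 h trough | C(3.5 h) / C(14 h) | Misclassified as written (CV 40%–30%) |
|---|---|---|---|
| 12 h | 3.4 | 1.8 | 33–37% |
| 16 h | 2.5 | 1.6 | 27–32% |
| 24 h | 1.8 | 1.35 | 21–26% |
| 36 h | 1.5 | 1.2 | 17–21% |
| 48 h | 1.35 | 1.2 | 15–19% |

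**Remedies in the same model, half-lives 12–24 h:**
- Centre log concentration within the three groups that date and approximate time can separate (this morning, last evening, yesterday morning), with no change in sampling: 13–18%.
- Sample morning dosers pre-dose (70% at 22–26 h, 30% still at 11–17 h) but pool as now: 13–20%.
- Do both, pre-dose draw and adjustment for time after dose: 8–12% (10–14% at 36–48 h).

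What remains after the last step comes mainly from residual error, so not all of the as-written figure is due to timing. A separate calculation isolates timing: no residual error, half sampled at 1–6 h and half at 10–18 h, CV 30% or 50%, ka 0.7 or 1.5. It gives 19–32% at a 12 h half-life, 9–18% at 24 h and 5–10% at 48 h, and zero if all samples share one time after dose.

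**Effect on the odds ratio.** Suppose CBR is 40% in the truly high half and 20% in the truly low half (assumed), and a fraction m is misclassified regardless of outcome. The observed rates are 0.40(1 − m) + 0.20m and 0.20(1 − m) + 0.40m.
- m = 0: 0.40 v 0.20, OR 2.67
- m = 0.1: 0.38 v 0.22, OR 2.17
- m = 0.2: 0.36 v 0.24, OR 1.78
- m = 0.3: 0.34 v 0.26, OR 1.47

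**Precision.** With 22 v 22 subjects, SE(log OR) = √(1/8.8 + 1/13.2 + 1/4.4 + 1/17.6) = 0.688. The 95% interval around 2.67 is about 0.7 to 10.

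**The case against.** The strongest reply is that the protocol already collects enough for a useful correction. Draw time is exact, and the last dose has a date and an approximate time. Section 11 defers analysis detail to a separate SAP, which is not among the supplied text. This largely stands. A reader might infer that approximate dose times cannot repair the problem, but grouping by them removes much of it in the model. What does not stand is leaving it there: the wording lets a site comply with two categories, and the analyses that are written down use neither.

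The size also rests on assumed pharmacokinetics. With a long half-life the effect is modest. The 8–12% further depends on half-life varying with clearance. If half-life is held fixed, sampling everyone pre-dose gives 12–16%.

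A reader might infer that the timing effect rivals the two-fold dose difference between arms. Peak against 24 h trough is the extreme pairing. The more typical morning-against-evening contrast is 1.2–1.8, the split is made within each arm, and no comparison of arms is intended.

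A reader might also infer that 9 mg concentrations will enter the 18 mg PK summary after dose reductions. Sections 4 and 11.4.1 set allocation rules for efficacy and safety only, and no rule is stated for PK. That one sentence in Section 6.4 does not name reductions does not show that they go unrecorded. In the exposure analysis, a low value after a reduction is genuine low exposure. The narrower gap is that the amount taken before the sample is not requested; the returned-capsule counts in Section 6.5 give totals between visits.

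Finally, with at most 44 subjects per arm, sampling error in the odds ratio exceeds the attenuation. That bears on severity, not on whether the defect exists.

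**Conclusion.** The point holds as a minor one. As written, samples at weeks 6, 18 and 24 may fall anywhere in the dosing interval, and both planned analyses ignore this. Exposure groups therefore partly reflect sampling time, and the concentration–CBR association is attenuated if timing is unrelated to outcome. The 21–37% (half-lives of 12–24 h) and 15–21% (36–48 h) are illustrations resting on the assumed model, variability and sampling mix; none of these inputs comes from the protocol.

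The documents do not support reading this as a threat to the efficacy conclusion. The two-stage test of CBR uses no concentration data. Only the descriptive PK objective and one tertiary analysis are affected.

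**What to change.** **Sections 7.3 and 8.2.2, and footnote 11 (both copies of the schedule).** For each PK sample after baseline, record the date and clock time (hh:mm) of the last dose and the number of capsules taken. Where practical, draw the sample before that day's dose for subjects who dose in the morning, as at baseline.

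**Section 11.4.3.6.** Summarise concentrations by time-after-dose band and by dose actually taken.

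**Section 11.4.3.4.** Adjust concentration for time after dose before the median split, or include time after dose in the model. Do not restrict to the pre-dose band: with 30% evening dosers (assumed) that would drop about 0.30 × 44 ≈ 13 subjects from a full arm.

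The sampling change and the adjustment belong together, since the pre-dose draw alone leaves 13–20% misclassified in the model at half-lives of 12–24 h.

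**Cost.** Two eCRF fields, a little extra analysis, and morning dosers taking that day's dose after the draw on three visit days. Supply should not be an obstacle, because Section 6.1.2 says "Subjects will be requested to bring with them the carton box with all blister packs at every visit". The data-collection part should be in place before sampling starts.
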